8.1.4 Procedures for Handling Missing, Unused, and Spurious Data

All available efficacy and safety data will be included in data listings and tabulations. The relevance of missing sample data will be assessed. Details on any sensitivity analyses and data handling details regarding issues such as missing data will be discussed in the SAP.

Data that are potentially spurious or erroneous will be examined according to standard data management operating procedures.

8.1.5 Demographic and Baseline Characteristics

Demographic and baseline characteristics will be summarized, including gender, age, race, weight, height, primary diagnosis, and other parameters as appropriate. No inferential statistics will be carried out.

8.1.6 Efficacy Analysis

All primary efficacy evaluations for the primary and key secondary efficacy endpoints will be conducted using the ITT population. In addition, sensitivity analysis may be performed using the all-enrolled population, per-protocol population, or response-evaluable population.

8.1.6.1 Analysis of Primary Efficacy Endpoints

The primary endpoint, ORR4, proportion of patients achieving an objective response that lasts at least 4 months, per IRF, will be analyzed using a Cochran-Mantel-Haenszel test stratified by baseline disease diagnosis (pcALCL or MF) based on ITT population. Details are described in the SAP. The 95% confidence interval of the difference in ORR4 between the 2 treatments will be provided.

The primary analysis will be based on the ITT population. The same analysis for the primary endpoint will be performed using the all-enrolled population, and PP population. Sensitivity analyses will be performed for ORR per IRF and ORR per investigator's assessment as well as objective response that lasts at least 4 months defined by the response criteria used for romidespin approval and published by Whittaker 2010.⁽²¹⁾

8.1.6.2 Analyses of Secondary Efficacy Endpoints

CR rate, progression-free survival, and changes in symptom domain per Skindex-29 assessment tool are designated as key secondary endpoints. A fixed sequential testing procedure will be used to test between the primary endpoint and the key secondary

Brentuximab vedotin (SGN-35)**Clinical Study Protocol C25001 Amendment 5, EudraCT: 2010-024215-14**

endpoints; that is, the key secondary endpoints will be tested only if the primary endpoint is statistically significant. To test the key secondary endpoints, a weighted Holm's procedure will be used. Details of the testing procedure will be fully described in the SAP.

Comparison of the CR rates between the 2 treatment groups will be conducted using the stratified Cochran-Mantel-Haenszel test. The 95% confidence interval of the difference of the response rates between the 2 treatments will also be provided.

PFS is defined as the time from randomization until disease progression or death due to any cause, whichever occurs first. Detailed rules of handling missing assessments and censoring for the analysis of PFS are described in the SAP. Stratified log-rank test statistics will be used to compare PFS between the 2 treatment arms. The hazard ratios along with the 95% CIs will be estimated using a stratified Cox regression model. The Kaplan-Meier method will be used to estimate the distribution of PFS for each treatment. Median times (if estimable), along with the 2-sided 95% CIs will be presented.

Comparison of symptom reductions between the 2 treatment arms will be conducted using the ANCOVA model controlling for baseline covariates. Symptom reduction is defined for each patient as the maximum reduction from baseline. A longitudinal model will be used for the sensitivity analysis. Missing data will be imputed with mean if there is no more than 1 missing item. Sensitivity analysis will be performed to evaluate impacts of missing data imputation.

Other secondary efficacy endpoints include EFS, duration of response, and duration of skin response. EFS is defined as the time from randomization until any cause of treatment failure: disease progression, discontinuation of treatment for any reason, or death due to any cause, whichever occurs first. Duration of response in subjects with confirmed response is the time between first documentation of response and disease progression. Duration of skin response is the time between the first skin response to progressive disease in skin. Stratified log-rank test statistics will be used to compare EFS between the 2 treatment arms. The hazard ratios along with the 95% CIs will be estimated using a stratified Cox regression model. The Kaplan-Meier method will be used to estimate the distribution of EFS for each treatment. Median times (if estimable), along with the 2-sided 95% CIs will be presented. Duration of response and duration of skin response will be summarized descriptively using the Kaplan-Meier method.

8.1.7 Analyses of Patient-Reported Outcomes and Health Economics

Analyses of patient reported outcomes and health economics will be performed using the ITT population.

8.1.7.1 Patient-Reported Outcomes Analysis

Patient-reported outcome assessments using the FACT-G and Skindex-29 subscale surveys will be analyzed to determine if response to therapy and side effects of therapy are accompanied by measurable changes in PROs. The analysis will be performed on summary scores as well as on subscales with specific analytical methods outlined in a formal statistical analysis plan developed prior to database lock.

The analysis of symptom reduction (Skindex-29) is described in Section [8.1.6.2](#).

Other subscales of the Skindex-29 questions will be summarized descriptively.

Global score and subscales of FACT-G will be summarized descriptively. Investigation of missing data patterns and imputation, if appropriate, will be discussed in statistical analysis plan.

8.1.7.2 Health Economics Analysis Using Healthcare Utilization and Utility

CCI

8.1.8 Pharmacokinetics/Pharmacodynamics/Biomarkers

8.1.8.1 Pharmacokinetic Analysis

The pharmacokinetics of the antibody drug-conjugate (brentuximab vedotin) and unconjugated drug (MMAE) will be derived from serum and plasma concentrations (respectively) versus time data for all patients who met study inclusion criteria, received study drug, and provided evaluable PK data. Population PK parameters will be calculated with an appropriate method based on a validated pharmacokinetic analysis program. Exploratory efficacy PK, and if possible, PK-pharmacodynamic relationship, will be determined.

8.1.8.2 Immunogenicity Analysis

All patients who were administered at least 1 dose of brentuximab vedotin will be evaluated for antitherapeutic antibody (ATA) development. A list/table of ATA status will be

Brentuximab vedotin (SGN-35)

Clinical Study Protocol C25001 Amendment 5, EudraCT: 2010-024215-14

provided. Antibody neutralizing status (neutralizing or not neutralizing) will also be listed for patients who have positive antibody status.

Immunogenicity information, including ATA and neutralizing ATA, will be summarized in descriptive statistics as applicable.

8.1.8.3 Pharmacodynamic Analysis

CCI

A large black rectangular redaction box covers the majority of the page content under section 8.1.8.3. The text 'CCI' is visible in the top-left corner of this redacted area.

8.1.8.4 Biomarker Analysis

CCI

A large black rectangular redaction box covers the majority of the page content under section 8.1.8.4. The text 'CCI' is visible in the top-left corner of this redacted area.

8.1.9 Safety Analysis

Safety will be evaluated by the incidence of AEs, severity and type of AEs, and by changes from baseline in the patient's vital signs, ECOG performance status, and clinical laboratory results using the safety population. Exposure to study drug and reasons for discontinuation will be tabulated.

Treatment-emergent AEs that occur after administration of the first dose of study drug and through 30 days after the last dose of study drug will be tabulated. Adverse events will be tabulated according to the Medical Dictionary for Regulatory Activities (MedDRA) and will include the following categories:

- TEAEs
- Study drug-related TEAEs
- Grade 3 or higher TEAEs

Brentuximab vedotin (SGN-35)

Clinical Study Protocol C25001 Amendment 5, EudraCT: 2010-024215-14

- Grade 3 or higher study drug-related TEAEs
- The most commonly reported treatment-emergent AEs (ie, those events reported by $\geq 10\%$ of all patients)
- SAEs

A listing of treatment-emergent AEs resulting in study drug discontinuation will be provided.

Descriptive statistics for both the actual values and change from the baseline assessment values of the clinical laboratory parameters (hematology and chemistry) will be presented for all scheduled measurements over time. Mean laboratory values over time will be plotted for key laboratory parameters. Shift tables for laboratory parameters will be generated based on changes in NCI CTCAE grade from the baseline assessment to the worst postbaseline value.

Descriptive statistics for the actual values (and/or the changes from the baseline assessment) of vital signs over time will be tabulated by scheduled time point.

Eastern Cooperative Oncology Group performance status and change from baseline will be summarized. Shifts from baseline to the worst postbaseline score will be tabulated by treatment group. Patients who have ECOG performance scores that worsen postbaseline compared to baseline will be listed with other pertinent patient information.

Investigators' assessments of ECG monitoring (normal, abnormal and clinically significant, or abnormal and not clinically significant), including unscheduled or retested measurements, will be presented in a listing.

Additional safety analyses may be performed to most clearly enumerate rates of toxicities and further define the safety profile of study drug.

9. STUDY COMMITTEES

9.1 Independent Data Monitoring Committee

An Independent Data Monitoring Committee (IDMC) will be established to review safety data according to a pre-specified IDMC charter. The first formal safety review will occur

after approximately 30 patients have been randomized in total and received at least 1 cycle of study treatment, or 6 months after the first patient is randomized (whichever comes first). Thereafter, IDMC safety reviews will be performed periodically per the IDMC charter.

10. ADVERSE EVENTS

10.1 Definitions

10.1.1 Pretreatment Event Definition

A pretreatment event is any untoward medical occurrence in a patient or subject who has signed informed consent to participate in a study but before administration of any study medication; it does not necessarily have to have a causal relationship with study participation.

10.1.2 Adverse Event Definition

Adverse event (AE) means any untoward medical occurrence in a patient or subject administered a pharmaceutical product; the untoward medical occurrence does not necessarily have a causal relationship with this treatment. An AE can therefore be any unfavorable and unintended sign (including an abnormal laboratory finding), symptom, or disease temporally associated with the use of a medicinal (investigational) product whether or not it is related to the medicinal product. This includes any newly occurring event, or a previous condition that has increased in severity or frequency since the administration of study drug.

An abnormal laboratory value should not be assessed as an AE unless that value leads to discontinuation or delay in treatment, dose modification, therapeutic intervention, or is considered by the investigator to be a clinically significant change from baseline.

10.1.3 Serious Adverse Event Definition

Serious AE (SAE) means any untoward medical occurrence that at any dose:

- Results in **death**.
- Is **life-threatening** (refers to an AE in which the patient was at risk of death at the time of the event. It does not refer to an event which hypothetically might have caused death if it were more severe).

Brentuximab vedotin (SGN-35)

Clinical Study Protocol C25001 Amendment 5, EudraCT: 2010-024215-14

- Requires inpatient **hospitalization or prolongation of an existing hospitalization** (see [clarification](#) in the paragraph below on planned hospitalizations).
- Results in **persistent or significant disability or incapacity**. (Disability is defined as a substantial disruption of a person's ability to conduct normal life functions).
- Is a **congenital anomaly/birth defect**.
- Is a **medically important event**. This refers to an AE that may not result in death, be immediately life threatening, or require hospitalization, but may be considered serious when, based on appropriate medical judgment, may jeopardize the patient, require medical or surgical intervention to prevent 1 of the outcomes listed above, or involves suspected transmission via a medicinal product of an infectious agent. Examples of such medical events include allergic bronchospasm requiring intensive treatment in an emergency room or at home, blood dyscrasias or convulsions that do not result in inpatient hospitalization, or the development of drug dependency or drug abuse; any organism, virus, or infectious particle (eg, prion protein transmitting Transmissible Spongiform Encephalopathy), pathogenic or nonpathogenic, is considered an infectious agent.

In this study, intensity for each AE, including any lab abnormality, will be determined using the NCI CTCAE, Version 4.03, effective date 14 June 2010.⁽⁴²⁾ Clarification should be made between a serious AE (SAE) and an AE that is considered severe in intensity (Grade 3 or 4), because the terms serious and severe are NOT synonymous. The general term *severe* is often used to describe the intensity (severity) of a specific event; the event itself, however, may be of relatively minor medical significance (such as a Grade 3 headache). This is NOT the same as *serious*, which is based on patient/event outcome or action criteria described above, and is usually associated with events that pose a threat to a patient's life or ability to function. A severe AE (Grade 3 or 4) does not necessarily need to be considered serious. For example, a white blood cell count of less than 1,000/mm³ to 500/mm³ is considered Grade 3 (severe) but may not be considered serious. Seriousness (not intensity) serves as a guide for defining regulatory reporting obligations.

10.2 Procedures for Recording and Reporting Adverse Events and Serious Adverse Events

All AEs spontaneously reported by the patient and/or in response to an open question from study personnel or revealed by observation, physical examination, or other diagnostic

Brentuximab vedotin (SGN-35)

Clinical Study Protocol C25001 Amendment 5, EudraCT: 2010-024215-14

procedures will be recorded on the appropriate page of the eCRF (see Section 10.3 for the period of observation). Any clinically relevant deterioration in laboratory assessments or other clinical finding is considered an AE. When possible, signs and symptoms indicating a common underlying pathology should be noted as 1 comprehensive event.

Regardless of causality, SAEs and serious pretreatment events (as defined in Section 10.1) must be reported (see Section 10.3 for the period of observation) by the investigator to the Millennium Department of Pharmacovigilance or designee (contact information provided below). This should be done by faxing the SAE Form within 24 hours after becoming aware of the event. The SAE Form, created specifically by Millennium, will be provided to each clinical study site. A sample of the SAE Form may be found in the Study Manual. Follow-up information on the SAE or serious pretreatment event may be requested by the Millennium Department of Pharmacovigilance or designee. SAE report information must be consistent with the data provided on the eCRF.

SAE Reporting Contact Information

CCI

Planned hospital admissions or surgical procedures for an illness or disease that existed before the patient was enrolled in the trial are not to be considered AEs unless the condition deteriorated in an unexpected manner during the trial (eg, surgery was performed earlier or later than planned).

For both serious and nonserious AEs, the investigator must determine both the intensity of the event and the relationship of the event to study drug administration. For serious pretreatment events, the investigator must determine both the intensity of the event and the relationship of the event to study procedures.

Intensity for each AE, including any lab abnormality, will be determined using the NCI CTCAE, Version 4.03, effective date 14 June 2010.⁽⁷⁴⁾ The criteria are provided in the Study Manual and also are available online at <http://ctep.cancer.gov/reporting/ctc.html>.

Relationship to study drug administration will be determined by the investigator responding yes or no to this question: Is there a reasonable possibility that the AE is associated with the study drug?

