The clinical laboratory parameters for which the most patients had new or worsening shifts to \geq Grade 3 were low neutrophils (11%), lymphocytes (11%), platelets (6%), leukocytes (5%), and high glucose (6%). Only 1 patient in the phase 2 studies had Grade 3 ALT and aspartate aminotransferase (AST).

In the phase 2 studies, 31% of patients had a serious adverse event (SAE), 28% had an SAE of Grade 3 or higher, and 15% had an SAE that was determined by the investigator to be related to brentuximab vedotin. The most common SAEs, reported in \geq 2% of patients, were abdominal pain, disease progression (recurrent sALCL), pulmonary embolism, and septic shock. A higher proportion of sALCL patients experienced SAEs, including deaths within 30 days of last dose, relative to HL patients, likely due to the older age and more aggressive nature of the malignancy in this patient population.

Brentuximab vedotin (SGN-35)

Clinical Study Protocol C25001 Amendment 5, EudraCT: 2010-024215-14

A total of 9 deaths were reported within the safety evaluation period (within 30 days of the last dose of brentuximab vedotin) in 357 patients across the 6 phase 1 and phase 2 studies for which data are available. Two patient deaths (0.6%) were considered related to study treatment. One patient in study SG035-0001 who received 3.6 mg/kg in phase 1 died due to febrile neutropenia and presumed septic shock. A second treatment-related death in study SG035-008A was attributed to pancytopenia, cytomegalovirus (CMV) infection, and intracranial hemorrhage. The remaining on-study deaths were primarily related to disease progression in sALCL patients.

Brentuximab vedotin has been shown to induce durable remissions in patients with HL both pre- and post-ASCT, and in patients with relapsed or refractory sALCL. Progression-free survival results comparing PFS with brentuximab vedotin to PFS from prior systemic therapy indicate that PFS is significantly prolonged with brentuximab vedotin for both HL and sALCL. A substantial number of HL and sALCL patients with B symptoms at baseline saw these symptoms resolve during treatment with brentuximab vedotin. In addition, the large majority of sALCL patients presenting with cutaneous lesions at baseline experienced resolution of these symptoms after receiving brentuximab vedotin.

Further details on clinical studies with brentuximab vedotin are provided in the brentuximab vedotin IB.

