5.8.2.1.2 Key Secondary Efficacy Analysis

Because a fixed sequential testing procedure is used between the primary endpoint and the key secondary endpoints, the key secondary endpoints will be tested only if the primary endpoint is statistically significant. The weighted Holm procedure⁽¹⁾ will be used for testing the key secondary endpoints. See Section 3.2 for details of the statistical decision rules.

Stratified log-rank test statistics will be used to compare PFS between the 2 treatment arms. The hazard ratios along with the 95% CIs will be estimated using a stratified Cox regression model. The Kaplan-Meier method will be used to estimate the distribution of the time-to-event endpoints for each treatment. Median times (if estimable), along with the 2-sided 95% CIs, will be presented.

Assuming the median PFS for the brentuximab vedotin treatment group and the physician's choice treatment group (MTX or bexarotene) are 9 and 6 months, respectively, the number of PFS events is projected to be approximately 101 at the time of the planned final analysis. This is based on an approximately 2-year enrollment period, a dropout rate of 10%, and an α level of 0.01 (2-sided), as specified in Section 3.2 per the weighted Holm procedure.

Comparison of the CR rates between the 2 treatment groups will be conducted using the stratified Cochran-Mantel-Haenszel test. The 95% CI of the difference in the response rates between the 2 treatments will also be provided. No imputation will be conducted for missing data. Patients who do not have any post baseline response assessment as specified in the protocol will be counted as nonresponders.

For skin symptoms (Skindex-29), the primary analysis will be comparing the mean symptom reduction between brentuximab vedotin and the control arms. 'Symptom reduction' is defined for each patient as the maximum reduction from baseline (sum of the 7 items related to skin symptoms normalized to a 1-100 scale). The analysis of covariance (ANCOVA) model controlling for baseline covariates (treatment group, baseline score, disease diagnosis, ECOG) will be employed for the analysis. As a sensitivity analysis, comparison of the 2 treatment groups will be conducted using the linear mixed model with repeated measures at

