5.11.1 Adverse Events

5.11.1.1 Adverse Events

Treatment-emergent AEs (TEAEs) will be tabulated by primary System Organ Class (SOC), High Level Term (HLT), and Preferred Term (PT). A TEAE is defined as any AE that occurs after administration of the first dose of study drug and up through 30 days after the last dose of study medication. AEs will be tabulated according to the most recent version (Version 8.1 or higher) of the Medical Dictionary for Regulatory Activities (MedDRA) by SOC, HLT, and PT and will include the following categories:

- TEAEs
- Study drug-related TEAEs
- Grade 3 or higher TEAEs
- Grade 3 or higher drug-related TEAEs
- TEAEs resulting in study drug discontinuation
- Serious AEs (SAEs), including study drug-related SAEs
- AEs of peripheral neuropathy identified by the broad search MedDRA SMQ "Peripheral neuropathy"

Additional analyses of peripheral neuropathy may also be presented.

The most commonly reported TEAEs (i.e., those events reported by $\geq 10\%$ of all patients) will be tabulated by HLT and PT.

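### Nothing exempts CTCL progression from the AE definition, so the all-causality safety totals can mix an efficacy outcome with toxicity

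*Protocol*

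**What the plan says.** **Protocol 10.1.2** extends the AE definition to a worsening of what was already there: "This includes any newly occurring event, or a previous condition that has increased in severity or frequency since the administration of study drug".

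**Protocol 10.2** adds: "Any clinically relevant deterioration in laboratory assessments or other clinical finding is considered an AE".

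**Limits on those rules.** Two come near this point, and neither reaches progression.
- Section 10.1.2 restricts laboratory values: "An abnormal laboratory value should not be assessed as an AE unless that value leads to discontinuation or delay in treatment", with a few further triggers. It does not restrict clinical findings.
- Section 10.2 sets aside "Planned hospital admissions or surgical procedures for an illness or disease that existed before the patient was enrolled in the trial", but not if the condition worsens unexpectedly.

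Section 10.2 also asks for signs of one underlying pathology to be recorded as one event. That governs grouping, not whether progression is recorded.

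**Window.** Under protocol 10.3, AEs are collected from first dose to 30 days after last dose. Under 4.1 and 7.7, progressive disease ends study treatment. Progression on treatment therefore falls inside the window.

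**SAP 5.11.1.1** says "A TEAE is defined as any AE that occurs after administration of the first dose of study drug", up to the same 30-day limit. It tabulates TEAEs, Grade 3 or higher TEAEs, TEAEs leading to discontinuation and SAEs by system organ class, high level term and preferred term. SAP 5.11.1.2 counts patients with at least one treatment-emergent SAE in the same layout.

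**SAP 5.8.2.1.2** assumes that the median PFS times for brentuximab vedotin and control "are 9 and 6 months, respectively".

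**The concern.** CTCL is a previous condition, and a new tumour or a rising skin score is a clinical finding. Read literally, clinically relevant progression on treatment meets the AE definition, and meets the SAE definition if it leads to hospitalisation or death. Protocol 10.1 to 10.3, protocol 8.1.9 and SAP 5.11.1 contain no exception.

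This has happened with this drug. Protocol 1.3 lists among the most common SAEs of the phase 2 studies, besides abdominal pain, "disease progression (recurrent sALCL), pulmonary embolism, and septic shock".

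In a single-arm study this is a matter of labelling. In a randomised comparison, progression is part of a key secondary endpoint and is planned to differ between arms. Any share of it that enters the safety totals adds a between-arm difference unrelated to drug toxicity. Sites know the treatment, and the documents do not tell them which way to record progression, so the share can vary by site and by arm.

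**Working it through.** **1. Does the exponential model match the plan?**

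Inputs: medians 9 and 6 months, about 2 years of enrolment and 10% dropout (SAP 5.8.2.1.2); 62 patients per arm (SAP 5.1); final analysis 10 months after the last patient is enrolled (protocol 4.3). Assumed: uniform accrual over 24 months and exponential dropout reaching 10% at 24 months.

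For each arm, with λ = ln 2/median and μ = -ln(0.9)/24, average λ/(λ+μ) × [1 - exp(-(λ+μ)t)] over follow-up t from 10 to 34 months. Multiply by 62 and add the arms.

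Result: 101.1 events, against about 101 in the SAP. With 10% dropout reached at 12 or 34 months instead, the result is 98.0 or 102.0. The model fits the plan.

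**2. PFS events inside the AE window**

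P(event by t) = 1 - 0.5^(t/median), with 30.4375 days per month.

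| Window | Brentuximab vedotin | Control | Gap |
|---|---|---|---|
| 48 weeks = 336 days = 11.04 months | 57.3% | 72.1% | 14.8 points |
| 48 weeks + 30 days = 366 days = 12.02 months | 60.4% | 75.1% | 14.7 points |

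The second row is about 37 and 47 patients of 62. It is a ceiling for a progression row. It assumes that every event is recorded as an AE, that everyone without an event is treated for the full 48 weeks, and that deaths, which PFS includes, count as progressions.

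**3. Effect on an any-event total**

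Let b be the share of patients who have another qualifying event, equal in both arms and independent of progression. Let q be the share of progressions recorded in that category. Both are assumptions.

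Arm total = 1 - (1 - b)(1 - qP), so the added gap = (1 - b) × q × 14.7 points.

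| Total | b (assumed) | q = 0.10 | q = 0.25 | q = 0.50 | q = 1.0 |
|---|---|---|---|---|---|
| Progression row alone | 0 | 1.5 | 3.7 | 7.3 | 14.7 |
| Any SAE | 31% | 1.0 | 2.5 | 5.1 | 10.1 |
| Any TEAE | 90% | 0.1 | 0.4 | 0.7 | 1.5 |

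The 31% is the SAE rate that protocol 1.3 gives for the phase 2 studies, applied here to both arms. For SAEs, q is the share of progressions recorded as serious, so q = 1 would mean that every progression is serious. At q = 0.10 to 0.25, the SAE gap is 0.6 to 1.6 patients of 62.

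For the Grade 3 or higher and discontinuation totals, backgrounds of 10% to 50% (assumed) give 1.3 down to 0.7 points at q = 0.10, and 3.3 down to 1.8 points at q = 0.25.

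**4. The opposing effect**

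If treatment ends at a PFS event or at 48 weeks, mean time on treatment = (median/ln 2) × P(event by 11.04 months).
- Brentuximab vedotin: 12.98 × 0.573 = 7.4 months.
- Control: 8.66 × 0.721 = 6.2 months.

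Adding 30 days (1.0 month) gives AE windows of 8.4 and 7.2 months. The control window is about 14% shorter (7.2/8.4 = 0.86), so that arm has less time to accrue other AEs.

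**The case against.** **Progression is already visible.** The SAP tabulates by preferred term and lists SAEs by patient. An event coded as progression has its own row, as the phase 2 summary shows by naming it. This stands. A reader might infer that the SAP never separates progression; that holds only for the any-event totals.

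**The literal reading goes too far.** The protocol treats progression as a disease outcome: it is scored by GRS, has its own line in the Schedule of Events, and is a reason for stopping treatment distinct from an adverse event (7.7). The 10.2 rule is also confined to clinically relevant deterioration. This stands in part. It makes it unlikely that sites will record every progression as an AE, but it is not an instruction to leave progression out. The Study Manual may give one; it is not among the documents reviewed.

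**The effect is small.** The recording share has no source. The only evidence is that progression was among SAEs seen in at least 2% of patients in other diseases. If 2-5% of brentuximab vedotin patients had a progression SAE (assumption), scaling by 0.721/0.573 = 1.26 gives a gap of 0.5 to 1.3 points, less than one patient of 62. The drug-related tables are filtered by the investigator's causality answer and are much less exposed. All of this stands.

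**The safety outputs are descriptive.** No safety test or alpha depends on them, and both documents allow additional safety analyses. That lowers the stakes, but an optional later analysis is weaker than a term list fixed before lock.

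**Conclusion.** The point holds in a limited form. The AE rules include clinically relevant CTCL progression on treatment, nothing exempts it, and the all-causality totals do not separate it from toxicity. The documents do not fix the size. About 15 points bounds a progression row only. Plausible effects on the totals are at most about 1.5 points for any TEAE (90% background assumed) and about 1 to 2.5 points for any SAE (31% background and 10-25% recording assumed). All of these rest on the SAP medians, exponential PFS, equal backgrounds and independence.

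A reader might infer that the safety tables will make control look about 15 points more toxic. The documents do not support that. The figure applies to one row, presumes complete recording and counts deaths. The shorter control AE window pulls the other way, so the net direction in the totals is not established.

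A reader might also infer that GRS-captured worsening should be removed from AE recording. That does not follow. Protocol 10.2 and 10.3 require SAEs to be in the eCRF and SAE reports to agree with it. Such a rule would also let an unblinded investigator's label of progression decide which safety data exist.

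This is a cheap improvement to presentation, not a flaw that threatens the trial's conclusions.

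**What to change.** In SAP 5.11.1.1 and 5.11.1.2:

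- Before database lock, and without sight of counts by arm, prespecify the preferred terms that describe progression of the CTCL under study, and flag them in the AE dataset.
- Present the any-event totals for TEAEs, Grade 3 or higher TEAEs, SAEs and TEAEs leading to discontinuation both with and without the flagged terms.

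Leave the AE and SAE recording and reporting rules in protocol 10.1 to 10.3 unchanged. The full tables then still show everything that sites recorded.

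Cost: one term list, one dataset flag and a few extra tables. Limitation: the flag catches only events coded to the listed terms. Disease symptoms coded under their own terms stay in both versions.
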